## 10.4 Routine Adverse Event Reporting

All Adverse Events **must** be reported in routine study data submissions. **AEs reported expeditiously through CTEP-AERS must also be reported in routine study data submissions.**

*The following paragraph only applies to trials using Medidata Rave; other trials may delete:*

Adverse event data collection and reporting, which are required as part of every clinical trial, are done to ensure the safety of patients enrolled in the studies as well as those who will enroll in future studies using similar agents. AEs are reported in a routine manner at scheduled times during the trial using Medidata Rave. For this trial the Adverse Event CRF is used for routine AE reporting in Rave.

## 10.5 Pregnancy

Although not an adverse event in and of itself, pregnancy as well as its outcome must be documented via **CTEP-AERS**. In addition, the **Pregnancy Information Form** included within the NCI Guidelines for Adverse Event Reporting Requirements must be completed and submitted to CTEP. Any pregnancy occurring in a patient or patient's partner from the time of consent to 90 days after the last dose of study drug must be reported and then followed for outcome. Newborn infants should be followed until 30 days old. Please see the "NCI Guidelines for Investigators: Adverse Event Reporting Requirements for DCTD (CTEP and CIP) and DCP INDs and IDEs" (at [http://ctep.cancer.gov/protocolDevelopment/adverse\\_effects.htm](http://ctep.cancer.gov/protocolDevelopment/adverse_effects.htm)) for more details on how to report pregnancy and its outcome to CTEP.

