- 3.1.12 WBC must be  $\leq 25,000$  at time of Day 1 of study treatment. Cytoreduction with Hydrea and leukapheresis is allowed.
- 3.1.13 Risks from venetoclax and nivolumab to the developing human fetus cannot be ruled out. For this reason and because decitabine is known to be teratogenic, women of child-bearing potential and men must agree to use adequate contraception (hormonal or barrier method of birth control; abstinence) prior to study entry and for the duration of study participation. Should a woman become pregnant or suspect she is pregnant while she or her partner is participating in this study, she should inform her treating physician immediately. Contraception use should be continued 6 months after the completion of all study treatments for

women of child bearing potential. Men treated or enrolled on this protocol must also agree to use adequate contraception prior to the study, for the duration of study participation, and 7 months after completion of decitabine, venetoclax, or nivolumab administration.

3.1.14 Ability to understand and the willingness to sign a written informed consent document. Patients with impaired decision-making are allowed to participate as long as the patient has a Legally Authorized Representative (LAR) or caregiver.

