## 6.5 Duration of Therapy

In the absence of treatment delays due to adverse event(s), treatment may continue until one of the following criteria applies:

- Disease progression/loss of response
- Bone marrow/stem cell transplantation
- Intercurrent illness that prevents further administration of treatment
- Unacceptable adverse event(s)
- Patient decides to withdraw from the study
- General or specific changes in the patient's condition render the patient unacceptable for further treatment in the judgment of the investigator
- Clinical progression
- Patient non-compliance
- Pregnancy
  - All women of child bearing potential should be instructed to contact the investigator immediately if they suspect they might be pregnant (e.g., missed or late menstrual period) at any time during study participation.
  - The investigator must immediately notify CTEP in the event of a confirmed pregnancy in a patient participating in the study.
- Termination of the study by sponsor
- The drug manufacturer can no longer provide the study agent

The reason(s) for protocol therapy discontinuation, the reason(s) for study removal, and the corresponding dates must be documented in the Case Report Form (CRF).

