
Serious adverse events that occur more than 30 days after the last administration of investigational agent/intervention and have an attribution of possible, probable, or definite require reporting as follows:
 
Expedited 24-hour notification followed by complete report within 5 calendar days for:
 
 
• All Grade 3, 4, and Grade 5 AEs
 
 
Expedited 10 calendar day reports for:
 
 
• Grade 2 AEs resulting in hospitalization or prolongation of hospitalization
 
 
For studies using PET or SPECT IND agents, the AE reporting period is limited to 10 radioactive half-lives, rounded UP to the nearest whole day, after the agent/intervention was last administered. Footnote “1” above applies after this reporting period.
		

Effective Date: May 5, 2011
		

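### Mandatory pregnancy reporting in Section 10.5 stops 90 days after the last dose, earlier than the 6- and 7-month post-treatment contraception periods in Section 3.1.13

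*Combined protocol and SAP*

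**What the plan says.** Section 10.5 covers "Any pregnancy occurring in a patient or patient's partner" and sets the period as "from the time of consent to 90 days after the last dose of study drug must be reported", with follow-up to outcome. Newborns are to be followed to 30 days of age.

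Section 3.1.13 opens its reasoning with "Risks from venetoclax and nivolumab to the developing human fetus cannot be ruled out" and adds that decitabine is known to be teratogenic. For women of child-bearing potential it states: "Contraception use should be continued 6 months after the completion of all study treatments". Men must agree to contraception during the study and for "7 months after completion of decitabine, venetoclax, or nivolumab administration".

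Two other provisions bear on late pregnancies:

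- Section 6.5, within the list of reasons for ending therapy: "The investigator must immediately notify CTEP in the event of a confirmed pregnancy in a patient participating in the study". It gives no time limit after the last dose and does not mention partners.
- The first footnote to the expedited reporting table in Section 10.3.4, which brings in "Serious adverse events that occur more than 30 days after the last administration of investigational agent/intervention and have an attribution of possible, probable, or definite". A congenital anomaly is among the outcomes that the table counts as serious.

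**The concern.** The two rules share one rationale, possible harm to a fetus from drug exposure, but use different periods. For one purpose the protocol is cautious for 6 or 7 months after treatment. For the other it stops requiring information after 90 days. A conception in the fourth month after treatment falls inside the contraception period of either sex, but Section 10.5 does not require it to be reported or followed to outcome.

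What is at stake is fetal-safety information on a three-drug combination that Section 2.5.4 describes as novel. If late pregnancies come to notice only when something goes wrong, there is no count of exposed pregnancies against which to judge an abnormal outcome. Scheduled testing does not help here. The Section 11 calendar places pregnancy tests at screening and at the start of each treatment cycle, with none in the relapse/off-study column. After treatment, capture depends on patients telling the site and on the site having a duty to report.

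**Working it through.** The plan gives no figure for this point, so there is none to reproduce. The check compares the periods and then looks for another rule that fills the difference.

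**Inputs**

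- Reporting window after the last dose: 90 days (Section 10.5).
- Post-treatment contraception: m = 6 months for women and m = 7 months for men (Section 3.1.13).
- Days per month, d: not stated. Assumed 30.44 (365.25/12), varied from 28 to 31.

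**Formula**

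Share of the post-treatment contraception period outside the Section 10.5 window = (m × d − 90) / (m × d).

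**Results**

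| d (days) | Women: (6d − 90)/6d | Men: (7d − 90)/7d |
|---|---|---|
| 28 | 78/168 = 46% | 106/196 = 54% |
| 30 | 90/180 = 50% | 120/210 = 57% |
| 30.44 | 92.6/182.6 = 51% | 123.1/213.1 = 58% |
| 31 | 96/186 = 52% | 127/217 = 59% |

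The choice of month length makes little difference: about 3 of 6 months and 4 of 7 months are not covered.

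**Sensitivity to the denominator**

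Section 10.5 runs from consent, so time on treatment is fully covered. With T months from consent to last dose counted in, the share is (m × d − 90) / ((T + m) × d), at d = 30.44. T is an assumption.

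| T (months) | Women | Men |
|---|---|---|
| 0 | 51% | 58% |
| 3 | 34% | 40% |
| 6 | 25% | 31% |
| 12 | 17% | 21% |

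The percentage falls as treatment lengthens, but the uncovered time stays at about 93 days for women and 123 days for men.

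**Do other provisions fill the gap?**

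| Pregnancy after day 90 | Section 10.5 | Section 6.5 | Section 10.3.4, late SAEs |
|---|---|---|---|
| Patient, uncomplicated | Not required | Only if participation includes follow-up; notification, not outcome follow-up | No |
| Partner, uncomplicated | Not required | Partners not named | No |
| Serious outcome with at least possible attribution | Not required | As above | May capture the event |

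**When the clock starts**

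Section 10.5 counts from the last dose of study drug, in the singular. Section 3.1.13 counts a woman's 6 months from the end of all study treatments. Section 9.1 uses the term study drug for nivolumab alone, and Sections 6.3, 7.5 and 7.6 allow a patient to stop nivolumab and stay on decitabine and venetoclax. Read literally with that usage, the 90 days could run out while decitabine is still being given.

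**The case against.** The strongest reply is that the two rules serve different purposes and can both be obeyed. A contraception period can be set cautiously, while a reporting rule sets a minimum. That is right: the sections do not contradict each other, and this is a matter of alignment.

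The second reply is that a reader might infer that late pregnancies will go unreported, or are excluded from the safety database. The documents do not support that. Section 10.5 says what must be reported and does not bar later reports. Its opening requirement to document pregnancy and outcome through CTEP-AERS carries no time limit of its own, although the period is set two sentences later. Section 3.1.13 asks a woman to tell her physician if she becomes pregnant while she or her partner is on the study. Section 6.6 follows patients for up to 3 years from the start of therapy, so participation in Section 6.5 could be read to include follow-up. An attributed congenital anomaly could come in under the late-SAE rule. A pregnancy that begins by day 90 but is discovered later is also still covered. These points narrow the gap without closing it: telling the treating physician places no onward reporting duty on the site, Section 6.5 does not name partners, and the late-SAE rule concerns serious events and not pregnancy as such.

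Third, a reader might take the contraception period as a risk period declared by the protocol, with every conception in it regarded as exposed. The protocol does not say so. It gives a duration for contraception and cites fetal risk as the reason.

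Fourth, the percentages are shares of calendar time and not counts of pregnancies. At most 42 patients are planned, 19 of them women (16 + 3 in the planned enrollment table), and the number of child-bearing potential is not given. Few events are likely. This stands and limits the importance of the point.

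Finally, Section 10.5 refers to NCI guidelines that were not available for this review. The finding therefore concerns the protocol's own text and not every reporting duty a site may have.

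**Conclusion.** The point holds as a gap in what Section 10.5 requires. Its 90 days leave about 3 of 6 post-treatment months for women and 4 of 7 for men outside mandatory reporting and outcome follow-up. That is about 51% and 58% at 30.44 days per month (46–52% and 54–59% over months of 28 to 31 days). These shares apply to post-treatment time only. It would be wrong to read them as half of the whole period from consent, or as half of all pregnancies.

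Section 6.5 and the late-SAE rule may pick up some cases, but they do not clearly cover partner pregnancies or uncomplicated pregnancies after day 90. The conclusion assumes that no external guideline imposes a longer window. It takes no position on whether 6 or 7 months is the right length for contraception.

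The importance is minor: no endpoint, dose-limiting toxicity decision or analysis depends on it.

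**What to change.** Reconcile Sections 3.1.13, 6.5 and 10.5:

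- In Section 10.5, extend the window for reporting and outcome follow-up so that it is no shorter than the contraception periods stated in Section 3.1.13, for patients and partners alike. Tying it to that section by cross-reference keeps the two aligned if either is amended.
- In Section 10.5, state that the window runs from the last dose of any of the three study drugs, whichever is given last.
- In Section 6.5, refer to Section 10.5 so that it is clear whether follow-up counts as participation and that partner pregnancies are included.

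As the periods now stand, the window would lengthen from 90 days to about 183 days for women (93 more) and about 213 days for partners of men (123 more). The uncovered share would fall to zero.

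The cost is a sentence or two of protocol text and a small amount of extra reporting among at most 42 patients. Section 6.6 already provides for follow-up of up to 3 years from the start of therapy. No treatment rule changes, and no change to the contraception periods is proposed.

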## 10.6 Secondary Malignancy

A *secondary malignancy* is a cancer caused by treatment for a previous malignancy (e.g., treatment with investigational agent/intervention, radiation or chemotherapy). A secondary malignancy is not considered a metastasis of the initial neoplasm.

CTEP requires all secondary malignancies that occur following treatment with an agent under an NCI IND/IDE be reported expeditiously via CTEP-AERS. Three options are available to describe the event:

- Leukemia secondary to oncology chemotherapy (e.g., acute myelocytic leukemia [AML])
- Myelodysplastic syndrome (MDS)
- Treatment-related secondary malignancy

Any malignancy possibly related to cancer treatment (including AML/MDS) should also be reported via the routine reporting mechanisms outlined in each protocol. Given that this treatment protocol is for acute myeloid leukemia, it is not anticipated that any secondary leukemia or MDS should be reported.

## 10.7 Second Malignancy

A second malignancy is one unrelated to the treatment of a prior malignancy (and is **NOT** a metastasis from the initial malignancy). Second malignancies require **ONLY** routine AE reporting unless otherwise specified.

## 11. STUDY CALENDAR

Baseline evaluations are to be conducted within 10 days prior to start of protocol therapy. In the event that the patient's condition is deteriorating, laboratory evaluations should be repeated within 48 hours prior to initiation of the next cycle of therapy.

	Pre-Study	Induction cycle 1	Induction cycles 2-3 (If needed)	Maintenance cycles	Relapse/Off Study
Decitabine		D	D	D	
Nivolumab		N	N	N	
Venetoclax		V	V	V	
Informed consent	X				
Demographics	X				
Medical history	X				
Concurrent meds a	X	X	X	X	
Physical exam b	X	X	X	X	X
Vital signs c	X	X			X
Height	X				
Weight	X	X			X
Performance status d	X	X			X
Serum Chemistry e	X	X	X	X	X
CBC w/diff f	X	X	X	X	X
EKG	X				
Adverse event evaluation g	X	X	X	X	X
Pregnancy test h	X	X	X	X	
Bone marrow i	X	X	X	X	X
Correlative studies j	X	X	X	X	X

D: Decitabine will be given on Days 1-10 of Induction cycles and Days 1-5 of maintenance cycles

N: Nivolumab will be given on Day 15 of cycle 1 and Days 1 and 15 of all subsequent cycles

V: Venetoclax will be given on Days 1-28 of induction cycles and Days 1-21 of maintenance cycles. Dosing ramp-up on days 1-3 or 1-4 (based on concurrent use of CYP3A inhibitors as outlined in Section 6.3.1)

a: Concurrent medications should be assessed at screening and the beginning of each treatment cycle

b: Physical exam should be performed at Screening, Days 1 and 15 of every cycle and End of Treatment/Relapse

c: Vital signs should be performed at Screening, Days 1 and 15 of every cycle and End of Treatment/Relapse. Vitals signs include blood pressure, heart rate, temperature, oxygen saturation, and respiratory rate.

d: Performance status should be evaluated at Screening, Day 1 of each cycle of therapy, and End of Treatment/Relapse

e: Serum chemistry will include: Na, K, CO2, Cl, BUN, Cr, AST, ALT, AP, TB, TP, albumin, LDH, and uric acid should be performed at screening, pre-dose (within 4 hours prior to venetoclax administration), every 12 hours during venetoclax ramp-up period (see Appendix C for tumor lysis management guidelines), twice weekly otherwise during induction cycles and at the beginning of each maintenance cycle and relapse/EOT

f: CBC with differential. To be performed at screening, twice weekly during induction cycles, and at the beginning of each maintenance cycle and relapse/EOT.

g: Adverse event evaluation: will occur on Days 1 and 15 of every cycle and End of Treatment/Relapse

h: Pregnancy test will occur for women of childbearing potential at Screening and the beginning of each cycle of treatment

i: Bone marrow biopsies will occur at the end of each cycle of induction, then every 3 cycles (starting with cycle 6) and at relapse/EOT.

j: Please see study sample collection table at Section 5.1 and 11.1 for bone marrow and peripheral blood collection time details.

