### 2.3.2 Venetoclax

Venetoclax is a B-cell lymphoma-2 (BCL-2) inhibitor which is an anti-apoptotic protein.

Venetoclax is predominantly metabolized by CYP3A4/5. Venetoclax had no large effect on QTc interval (i.e., > 20 ms) and there was no relationship between venetoclax exposure and change in QTc interval. Gastric acid reducing agents (e.g., proton pump inhibitors, H2-receptor antagonists, antacids) do not affect venetoclax bioavailability. Avoid grapefruit products, Seville oranges, and starfruit during treatment.

There is also a risk of developing tumor lysis syndrome (TLS) with venetoclax. For prophylaxis, patients should be instructed to drink 6 to 8 glasses water each day, starting 2 days before the first dose, on the day of the first dose of venetoclax, and each time the dose is increased. Consider IV hydration and/or uric acid reducing agents in patients at risk for TLS.

The proposed dose for venetoclax is 400 mg daily with ramp-up to this dose during days 1-3 of cycle 1 and continue on 400mg on days 4-21 of cycle 1 (28 day cycle) with subsequent cycle doses of 400mg on days 1-21. Dose ramp up will be 100 mg on day 1 and 200 mg on day 2 followed by the goal dose of 400 mg on day 3 and onwards. There will be dose adjustments for venetoclax based on the FDA label if concurrent use with moderate or strong CYP3A inhibitors (See Section 6.3.1 and 6.3.1.1)

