## 6. TREATMENT PLAN

### 6.1 Agent Administration

Treatment will be administered as either an outpatient or inpatient basis as appropriate. Reported adverse events and potential risks are described in Section 10. Appropriate dose modifications are described in Section 7. No investigational or commercial agents or therapies other than those described below may be administered with the intent to treat the patient's malignancy.

Dose Scheduling			
Dose level	Venetoclax*	Decitabine	Nivolumab
Dose level -2	Cycle 1 Day 1 100mg Cycle 1 Day 2 200mg Cycle 1 Day 3-14 400mg  Cycle 2 and beyond Day 1-14 400mg	Induction 20 mg/m  intravenously on Days 1-10  Maintenance 20 mg/m  intravenously on Days 1-5	Flat dose of 240mg every 2 weeks starting on Day 15 of Cycle 1 and continue Day 1 and 15 with cycle 2 and subsequent cycles
Dose level -1	Cycle 1 Day 1 100mg Cycle 1 Day 2 200mg Cycle 1 Day 3-21 400mg  Cycle 2 and beyond Day 1-21 400mg		
Dose level 1	Cycle 1 Day 1 100mg Cycle 1 Day 2 200mg Cycle 1 Day 3-28 400mg  Cycle 2 and Cycle 3 (if needed) Day 1-28 400 mg  Maintenance cycles Day 1-21 400 mg		

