### Regimen Description

Agent	Premedications; Precautions	Dose	Route	Schedule	Cycle Length
Nivolumab	Take precaution for infusion/anaphylactic reaction	240mg in max of 160ml NS	IV over 30 minutes	Days 1 and 15 (day 15 only for cycle 1)	
Decitabine	Premedicate with ondansetron 30 minutes prior to chemotherapy	20 mg/m  in 150ml NS	IV over 60 minutes	Days 1-10 for induction cycles and Days 1-5 for maintenance cycles	28 days (4 weeks)
Venetoclax*	Take with a meal and water. Premedicate with allopurinol and adequate hydration.	Four 100 mg tablets	PO in the a.m.	Daily, days 1-28 (with ramp up for cycle 1 only – Day 1 100mg, Day 2, 200mg, and Day 3 400mg) [note: days 1-21 for maintenance cycles]	

\*Please see Section 6.4.1.1 for dose adjustments with concurrent CYP3A inhibitor use

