### 6.5.1 Duration of Therapy in cases of CR

If the patient achieves a CR/CRi, even if MRD negative, the patient should continue on therapy as long as none of the above instances in 6.5 occurs. However, venetoclax may be interrupted, and the subsequent cycle of decitabine may be delayed to allow for absolute neutrophil count recovery from day 29 of current cycle until absolute neutrophil count reached at least 500/ $\mu$ L or

up to 14 days, then a bone marrow biopsy should be done to assess for continued CR/CRi. If patient remains in CR/CRi then dose reductions can occur as follows. For recurrent Grade 4 neutropenia and thrombocytopenia that lasts >6 weeks from Day 1 of cycle: first dose reduction will be to decrease venetoclax to 14 days (days 1-14 of the cycle), the second dose reduction will be to decreased to 7 days (days 1-7 of the cycle), the third dose reduction will be to reduce decitabine to 4 days (days 1-4 of the cycle), and the fourth/final dose reduction will be to reduce decitabine to 3 days (days 1-3 of the cycle). If Grade 4 thrombocytopenia and neutropenia recurs after all of these four dose reductions and lasting >56 days, patient will be taken off study.

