# **7. DOSING DELAYS/DOSE MODIFICATIONS**

## **7.1 Dose Delays/Modifications for DLT**

Study treatment (all three drugs) will be held for any patients experiencing a DLT.

Non-hematologic DLT: Patients may restart therapy when the adverse event recovers to CTCAE  $\leq$ grade 1 or to the patient's baseline values. If study treatment is restarted and another non-hematologic DLT is encountered, the patient must be removed from the study.

Hematologic DLT: After the 42 day period and confirmed hematologic DLT: If peripheral blasts are absent AND the bone marrow blasts are less than 5%, then the patient may restart study treatment with decrease of decitabine to 5 days from 10 days of therapy.

If treatment is delayed >6 weeks for an adverse event the patient must be permanently discontinued from study therapy.

Patients requiring > two dose delays for the same event should go off protocol therapy.

Please see specific modifications for Nivolumab (Section 7.3)

Drugs may be resumed per protocol. If a specific agent (e.g. decitabine or nivolumab or venetoclax) is permanently discontinued for toxicity, the other two agents may be continued on study. Decitabine and venetoclax doses should not be reduced following toxicity and dose interruption, they should continue at the same dose as stated in the protocol.

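### Venetoclax days per cycle, the only difference between the dose levels, are stated inconsistently, and the first haematologic reduction step changes nothing at DL -2

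*Combined protocol and SAP*

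**What the plan says.** All three levels in the Section 6.1 dose table share one decitabine and one nivolumab schedule, so venetoclax days alone separate them. At DL 1 the table gives "Cycle 1 Day 3-28 400mg" after a two-day ramp-up, then "Cycle 2 and Cycle 3 (if needed) Day 1-28 400 mg", and 21 days in maintenance. At DL -1 every cycle ends on day 21. At DL -2 cycle 1 ends on day 14, followed by "Cycle 2 and beyond Day 1-14 400mg".

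Four other places state venetoclax days without reference to a dose level:

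- **Schema:** to day 28 in induction, to day 21 in maintenance.
- **Regimen Description (also under 6.1):** days 1-28, with the bracketed remark "note: days 1-21 for maintenance cycles".
- **Section 11, calendar footnote V:** "Venetoclax will be given on Days 1-28 of induction cycles and Days 1-21 of maintenance cycles".
- **Section 2.3.2:** "continue on 400mg on days 4-21 of cycle 1 (28 day cycle) with subsequent cycle doses of 400mg on days 1-21".

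On toxicity, Section 6.5.1 sets out four steps for recurrent, prolonged grade 4 cytopenia in patients who remain in CR/CRi. It begins: "first dose reduction will be to decrease venetoclax to 14 days (days 1-14 of the cycle". Section 7.2 repeats the ladder for haematologic adverse events without the CR/CRi limit. Neither section ties the steps to the assigned level. Sections 7.1 and 7.2 also each contain a sentence ruling out reduction of decitabine or venetoclax after toxicity and interruption. In 7.2 that sentence comes directly before the list of reductions.

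**The concern.** The primary objective is safety and the MTD, found by a 3+3 design over DL 1, -1 and -2. The quantity being varied is the number of venetoclax days, and only one table carries the variation. The lower levels open only if DL 1 is not tolerated. A site that then doses from the calendar, the Schema or the Regimen Description gives the DL 1 schedule to patients assigned less.

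The DLT counts would be attributed to a level that was not delivered, and both the declared MTD and the 30-patient cohort treated at it could describe a different schedule. The reduction ladder has a related fault: its first step is written as an absolute number of days, and that number is already the DL -2 schedule.

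**Working it through.** **The plan's own figure.** Section 9.1 declares the combination promising with at least 13 responses in 30, testing 0.30 against 0.50. By the exact binomial, P(X ≥ 13 | n = 30, p = 0.30) = 0.0845 and P(X ≤ 12 | n = 30, p = 0.50) = 0.1808. These match the stated 0.084 and 0.181. They do not depend on venetoclax days, so this point leaves them unchanged.

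**Days per cycle, source by source**

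| Source | Induction | Maintenance | Conflict with the 6.1 dose table |
|---|---|---|---|
| Dose table, DL 1 | 28 | 21 | – |
| Dose table, DL -1 | 21 | 21 | – |
| Dose table, DL -2 | 14 | 14 | – |
| Schema, Regimen Description, footnote V | 28 | 21 | DL -1 in induction; DL -2 in all cycles |
| Section 2.3.2 | 21 | 21 | DL 1 in induction; DL -2 in all cycles |

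**Size over cycles 1 to 3.** The DLT window runs from cycle 1 day 15 to the end of cycle 3, so three cycles is the relevant span. A responder moves to maintenance when response is noted, so the calendar total depends on the number of induction cycles:

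- one induction, two maintenance: 28 + 21 + 21 = 70 days
- two induction, one maintenance: 28 + 28 + 21 = 77 days
- three induction: 28 + 28 + 28 = 84 days

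Assigned totals are 3 × 21 = 63 at DL -1 and 3 × 14 = 42 at DL -2, whatever the phase. The ratios of calendar days to assigned days are:

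- DL -1: 70/63 = 1.11, 77/63 = 1.22, 84/63 = 1.33
- DL -2: 70/42 = 1.67, 77/42 = 1.83, 84/42 = 2.0

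In maintenance alone, the calendar equals DL -1 (21/21 = 1.0) and exceeds DL -2 (21/14 = 1.5). At DL 1 the calendar and the dose table agree.

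Section 2.3.2 gives 63 days over the same span. At DL 1 that is 63/84 = 0.75 to 63/70 = 0.90 of the assigned days, and at DL -2 it is 63/42 = 1.5 times.

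**Check in milligrams.** Cycle 1 is 100 + 200 + 400 × (last day − 2), and later cycles are 400 × days. The calendar then gives 27,500 to 33,100 mg, against 24,700 mg at DL -1 (1.11 to 1.34 times) and 16,300 mg at DL -2 (1.69 to 2.03 times). The ramp-up barely changes the picture.

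**First reduction step, to 14 days**

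| Level and phase | From | To | Change |
|---|---|---|---|
| DL 1 induction | 28 | 14 | −14 days (50%) |
| DL 1 maintenance | 21 | 14 | −7 days (33%) |
| DL -1, any cycle | 21 | 14 | −7 days (33%) |
| DL -2, any cycle | 14 | 14 | 0 days |

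The second step, to 7 days, is a real reduction at every level.

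**The case against.** The strongest reply is that the effect is conditional. At DL 1, the starting level, the dose table, Schema, Regimen Description and calendar agree. Harm requires de-escalation and a site working from a summary. Section 9.1 points to Section 6.1 for the dose levels and the dosing schema, and Section 2.3.2 is background. This stands as a limit on likelihood. It does not remove the conflict, because the Regimen Description sits in Section 6.1 beside the dose table and no passage ranks one above the other.

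A reader might also infer more than the text supports, in four ways:

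- **That calendar dosing simply doubles DL -2 exposure, or returns every lower-level patient to the schedule that failed.** Two-fold is the upper end, reached only with three induction cycles. At DL -1 the calendar matches the assigned schedule in maintenance.
- **That the empty first step re-exposes a patient whose counts have not recovered.** Section 7.4 holds both drugs until neutropenia and thrombocytopenia improve, and Section 6.5.1 allows interruption for neutrophil recovery. Only the first of four steps is empty, and only at DL -2.
- **That the step in Section 7.1 after haematologic DLT, "then the patient may restart study treatment with decrease of decitabine to 5 days from 10 days of therapy", also reduces nothing.** The argument would be that marrow blasts under 5% with low counts means CRi, which already leads to 5-day maintenance. But Section 6.3 allows a haematologic DLT on haemoglobin alone, whereas CRi in Section 12.1 requires low neutrophils or platelets. A transfusion-dependent patient with those two counts recovered is not CRi, CR or CRh but fits MLFS. The Schema and Section 9.1 do not send MLFS to maintenance, so for that induction patient 10 to 5 days is a real reduction.
- **That the response test is mis-sized.** It is not; its error rates reproduce.

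**Conclusion.** The inconsistency is real and affects the variable that defines the MTD, so it is more than clerical. If a lower level opens and the calendar is followed, the excess over assigned venetoclax days in cycles 1 to 3 is 11% to 33% at DL -1 and 67% to 100% at DL -2. These figures assume that all three cycles are completed as scheduled, without holds, reductions or dose adjustment for CYP3A inhibitors. How often a site would dose from the calendar cannot be derived from the documents.

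Two further faults hold independently of that scenario. The first ladder step is a 0-day change at DL -2, and the sentences in Sections 7.1 and 7.2 ruling out reductions contradict the reductions in the same sections. The passages should be reconciled before DL -1 or DL -2 can open. The conflict between Section 2.3.2 and DL 1 induction is already present at the starting level.

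**What to change.** Reconcile the Schema, Section 2.3.2, the Section 6.1 dose table, the Regimen Description and calendar footnote V, so that venetoclax days are stated consistently for each assigned dose level and each phase. Reconcile the reduction text in Sections 6.5.1, 7.1 and 7.2 with the dose-level schedules and with the sentences that rule out reductions. The sponsor must decide which schedule and which steps apply; none is proposed here.

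The cost is amendment wording in about eight places. It needs no extra patients or procedures and no change to the sample size.
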